9.3.1 General Considerations

- Analysis software: Phoenix WinNonlin 7.0 software (or above) will be used to calculate pharmacokinetic parameters, and all other statistical analyses will be performed using SAS 9.4 software (or above).
- Baseline definition: the most recent measurement prior to the first dose of investigational drug is defined as baseline. If it is missing or cannot be determined then the screening period or baseline visit will be taken as baseline.
- Statistical descriptions: quantitative statistical descriptions include: number of cases (N), mean (Mean), standard deviation (S.D.), coefficient of variation (CV), median, quartiles (Q1/Q3), minimum (Min), maximum (Max), geometric mean, geometric S.D., geometric CV. Qualitative statistical descriptions include: frequency and percentages.

9.3.2 Participant Distribution, Demographics and Baseline Characteristics

The distribution of participants will be analyzed using SS. Number of participants screened, and the number and ratio of participants who failed screening with reasons will be listed. Calculate the number and ratio of participants enrolling, completing the study, and ending the study early and their reasons. Summarize protocol deviations by category and severity. Draw a flow chart of the distribution of participants.

Descriptive demographics and other baseline characteristics will be used.

9.3.3 Pharmacokinetic Analysis

Using PKCS, individual and mean concentration-time (c-t) curves and semi-log c-t curves will be plotted, and descriptive statistics will be used to list the mean, standard deviation, median, quartiles (Q1 and Q3), maximum, minimum, coefficient of variation, geometric mean, geometric standard deviation, and geometric coefficient of variation of the PK concentrations at the time points.

Pharmacokinetic parameters will be calculated for each participant by non-compartment model using PKPS with Phoenix WinNonlin 7.0 software (or above), including time to peak drug concentration (T_{max}), peak concentration (C_{max}), elimination half-life ($t_{1/2}$), mean residence time (MRT), area under the serum concentration-time curve from time zero to the last measurable serum concentration time t (AUC_{0-t}), area under the curve extrapolated from zero

to time of infinity ($AUC_{0-\infty}$), apparent volume of distribution (V_d/F), terminal elimination rate constant (K_e), apparent clearance (CL/F), and area ratio under extrapolated concentration-time curve ($AUC_{\%Extrap}$). When calculating pharmacokinetic parameters, samples with concentrations below the lower limit of quantification (LLOQ) prior to the C_{max} being reached should be treated as zero, and as not quantifiable (ND) for LLOQ samples after the C_{max} . Also, the arithmetic mean, standard deviation, coefficient of variation, median, quartiles (Q1 and Q3), maximum, minimum, geometric mean, geometric standard deviation, and geometric coefficient of variation will be calculated for pharmacokinetic parameters. For T_{max} , only the number of observations, median, minimum, and maximum will be listed. When $AUC_{\%Extrap} > 20\%$, $AUC_{0-\infty}$, $t_{1/2}$, K_e , and $AUC_{\%Extrap}$ will be not analyzed for descriptive statistics but only listed.

Because of the endogenous substance of TPO in this study, there may be cases of non-below quantitation limit (BQL) of concentration in blood samples before administration, if such cases occur, baseline correction is required before calculating the pharmacokinetic parameters, and the concentration value after administration minus the baseline value is used to calculate the PK parameter. If a negative value occurs in the process of calculation, and if the negative value occurs before or after quantifiable data, the negative value will be treated as 0. If the negative value occurs between two quantifiable data, it is treated as missing.

Agreement on out-of-window of key PK data points: deviations exceeding the maximum time range allowed for non-relevance under the protocol will be considered to be out of window, and all PK parameters will be calculated using the actual time of blood sampling, and the actual time of blood sampling will be used in plotting the serum concentration-time curve for each participant.

Phoenix WinNonlin 7.0 software (or above) will be used to calculate pharmacokinetic parameters, and all other statistical analyses will be done using SAS 9.4 software (or above).

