Unless otherwise specified, all statistical analyses will be performed using SAS 9.4 software (or above). In general, continuous variables will be described statistically using number of cases, mean, standard deviation, median, quartile, minimum, and maximum etc; categorical and rank variables will be described statistically using frequencies and percentages for each category or rank; missing values will not be included in the calculation of percentages unless otherwise specified. This is a Phase I exploratory clinical study of single-arm, single-dose administration. Descriptive statistical analysis will be mainly used without statistical inferences.

Demographic data and other baseline characteristics

Demographic data and other baseline characteristics will be summarized using descriptive statistics.

PK parameter analysis

Pharmacokinetic parameters will be calculated using Phoenix WinNonlin 7.0 software (or above) for fitting with noncompartmental analysis. The following pharmacokinetic parameters will be calculated based on the Pharmacokinetics Parameter Sets (PKPS): time to peak drug concentration (T_{max}), peak concentration (C_{max}), mean residence time (MRT), terminal elimination rate constant (K_e), area under serum concentration-time curve (AUC), apparent clearance (CL/F), apparent volume of distribution (V_d/F), elimination half-life ($t_{1/2}$), area ratio under extrapolated concentration-time curve ($AUC_{\% \text{ Extrap}}$), etc. Descriptive statistics will be performed for pharmacokinetic parameters, such as number of observations, arithmetic mean, standard deviation, coefficient of variation (CV%), median, quartiles (Q1 and Q3), minimum, maximum, geometric mean, geometric standard deviation and geometric CV%. For T_{max} , only the number of observations, median, minimum, and maximum will be listed.

PD indicator analysis

All analyses of pharmacodynamics will be based on the Pharmacodynamic Analysis Set (PDS).

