2.2 Background

2.2.1 Thrombopoietin and Recombinant Human Thrombopoietin (rhTPO)

Thrombopoietin (TPO) is an endogenous cytokine that stimulates the growth and differentiation of megakaryocytes, mainly produced by the liver, and produces biological effects by binding to its specific receptor c-mpl, i.e., it regulates megakaryocyte proliferation, differentiation, maturation, and splitting to form functional platelets. In vivo tests have shown that TPO can significantly stimulate platelet production and increase platelet count in peripheral blood^{[1][2][3]}. TPO also acts on early stem cells and expands the pool of targeted megakaryotic progenitor

cells^[4]. TPO also works synergistically with erythropoietin, stem cell factor, interleukin-3, granulocyte colony-stimulating factor, etc., to promote proliferation of erythroid and granulocytic progenitor cells, and to facilitate the entry of stem cells into the proliferative cycle^[5].

Recombinant human thrombopoietin, developed by 3SBio Inc., is a full-length glycosylated TPO expressed in CHO cells and purified, with a half-life of approximately 40 hours. rhTPO, which has a similar platelet-raising pharmacology to endogenous thrombopoietin, was approved for the treatment of CIT for solid tumors in 2005, and gained a second indication for the treatment of adult ITP in 2010. It was further approved in 2024 for the treatment of pediatric ITP in children over six years old. In addition, TPIAO[®] has been approved for marketing in the 9 other countries.

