9.3 Statistical Analyses

This section is a summary of the planned statistical analyses of the most important endpoints including primary and secondary endpoints.

There is no statistical hypothesis associated with the study objectives. As such, no statistical tests will be performed. The analyses of safety, efficacy, biomarker and pre-defined subgroups will primarily be descriptive.

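### The AUC%Extrap > 20% rule withholds AUC0-∞, t1/2 and Ke from the summaries but leaves in CL/F and Vd/F, which are calculated from them

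*Protocol*

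**What the plan says.** Section 9.3.3 names ten non-compartmental parameters, among them CL/F and Vd/F. All ten belong to the primary endpoint in section 3, Table 5. The default is full summary: "geometric mean, geometric standard deviation, and geometric coefficient of variation will be calculated for pharmacokinetic parameters", with a reduced set for Tmax only. The synopsis says the same ("Descriptive statistics will be performed for pharmacokinetic parameters, such as number of observations") and does not mention a 20% rule.

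The exception closes the second paragraph of 9.3.3. When AUC%Extrap is above 20%, four quantities (AUC0-∞, t1/2, Ke and AUC%Extrap) "will be not analyzed for descriptive statistics but only listed".

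Two other provisions bear on how often this could happen:
- Baseline is a single value: "the most recent measurement prior to the first dose of investigational drug is defined as baseline" (section 9.3.1).
- If endogenous TPO is measurable before dosing, "the concentration value after administration minus the baseline value is used to calculate the PK parameter" (section 9.3.3).

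**The concern.** The listed-only set is closed, and it stops short of the parameters that depend on its members. CL/F is a reciprocal of AUC0-∞. Vd/F is a reciprocal of Ke × AUC0-∞, so it carries both errors. If a participant's extrapolation is too large for AUC0-∞ and Ke to be summarised, the same reason applies to CL/F and Vd/F. The protocol gives no reason for treating them differently.

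If k participants are flagged, the summaries of CL/F and Vd/F include k more participants than those of AUC0-∞, t1/2 and Ke. The means, CVs and extremes would then not describe the same people. MRT has the same gap only if it is extrapolated to infinity, which the protocol does not state.

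**Working it through.** **Text check.** The exclusions elsewhere do not cover the gap. Table 8 (section 9.2) removes participants from the PK parameter set only for major protocol violations. The baseline-correction paragraph of 9.3.3 deals with negative values. The synopsis adds nothing. CL/F and Vd/F therefore stay in the summary for a flagged participant.

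**How the error carries over.** The identities are standard but not printed in the protocol: CL/F = Dose/AUC0-∞; Vd/F = Dose/(Ke × AUC0-∞); AUC%Extrap = 100 × (Clast/Ke)/AUC0-∞. Suppose the true extrapolated share is 30% and Ke is mis-estimated by a factor f (both assumed). Relative to truth:
- f = 0.5: AUC0-∞ = 0.7 + 0.3/0.5 = 1.30; CL/F = 1/1.30 = 0.77; Vd/F = 1/(1.30 × 0.5) = 1.54.
- f = 1.5: AUC0-∞ = 0.7 + 0.3/1.5 = 0.90; CL/F = 1/0.90 = 1.11; Vd/F = 1/(0.90 × 1.5) = 0.74.

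Vd/F is distorted more than the AUC0-∞ that is withheld.

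**Is the rule triggered on the protocol's figures?** Section 2.2.1 describes rhTPO "with a half-life of approximately 40 hours", so Ke = ln 2/40 = 0.0173/h. The last sample is at 312 h (Table 2). The mono-exponential share beyond it is exp(-0.0173 × 312) = 0.45%; a one-compartment model with absorption rate ka of 0.1 to 1.0/h (assumed) gives about 0.5%. To exceed 20%, the last measurable sample must fall before ln 5/0.0173 = 93 h, or the terminal half-life must exceed about 134 h with sampling to 312 h.

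**Route through baseline subtraction.** If the subtracted pre-dose value is too low, a constant residual remains. Without noise, with Table 2 times and a terminal fit on the last 3 to 5 points, a residual of 5.6% to 12.1% of Cmax brings AUC%Extrap to 20%. At that threshold the fitted Ke is 0.18 to 0.25 of truth, CL/F 0.55 to 0.63 and Vd/F 2.2 to 3.5 times truth. One such value among 22 otherwise undistorted participants moves the Vd/F geometric mean by about 2.2^(1/22) - 1 = 4% to 3.5^(1/22) - 1 = 6%.

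**Simulation.** The protocol does not give the ratio R of Cmax to endogenous baseline, or the assay CV; both are assumed here. There are 8,000 profiles per scenario, with half-life 40 h, ka 0.25/h and between-subject SD 0.25 (log scale). One pre-dose value is subtracted with the protocol's negative-value rule. Ke is taken from the best adjusted R² on at least 3 points after Cmax. Shifts compare the geometric mean under the rule as written with that after excluding flagged values.

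| R | CV | Flagged | CL/F shift | Vd/F shift |
|---|---|---|---|---|
| 2 | 20% | 22.2% | -7.0% | +10.4% |
| 2 | 10% | 4.5% | -0.8% | +2.7% |
| 5 | 20% | 3.2% | -0.5% | +2.3% |
| 5 | 10% | 0.2% | at most 0.1% | at most 0.6% |
| 10 | 20% | 0.4% | at most 0.1% | at most 0.6% |

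In the first three scenarios, 83% to 87% of flagged profiles run past 96 h with fitted Ke below 0.7 of truth; only 7% to 8% end at or before 96 h. So the slow tail, not early loss of signal, is the main route. Varying ka over 0.1 to 1.0/h and SD over 0.15 to 0.40 in the second and third scenarios gives trigger rates of 1.7% to 10.1%, CL/F shifts of -0.1% to -1.5% and Vd/F shifts of +1.2% to +6.6%.

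**The case against.** **This is detail for the SAP.** Reporting rules for derived PK parameters often sit there, and the SAP is not at hand. But the protocol did not leave this rule open: it fixed the threshold and the list. An SAP that follows the list repeats the gap, and one that completes it departs from the protocol. This objection does not remove the point.

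**It will hardly ever bite.** On the stated half-life and sampling the rule is not triggered, and every non-zero rate above rests on assumed inputs. This stands.

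**The simulation accepts poor terminal fits.** This also stands. If an adjusted R² of at least 0.8 is assumed as an acceptance criterion, the trigger rates in the first three scenarios fall to 5.6%, 2.1% and 1.4%, and the worst-case shifts fall to about -2% (CL/F) and +5% (Vd/F). The most adverse row is therefore an upper bound. The slow tail still accounts for 73% to 81% of flagged profiles under that criterion.

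**The effect is small and visible.** The standard error of the geometric mean at n = 22 is 7.5% to 10.9% in these simulations, above most of the shifts. No inference depends on the rule ("There is no statistical hypothesis associated with the study objectives"), N is reported ("quantitative statistical descriptions include: number of cases (N), mean (Mean"), and flagged values are listed. All of this stands. A visible difference in N does not, however, take the value out of the mean, CV or maximum.

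**The edit does not cure the main error.** Correct. Most of the error in flagged profiles comes from baseline subtraction. Their median AUC0-t, which stays summarised, is 16% to 28% above the true AUC0-∞ in the first three scenarios. After exclusion the CL/F geometric mean is still 0.86 to 0.93 of truth.

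**Conclusion.** The concern holds, as a minor one. Followed literally, section 9.3.3 summarises CL/F and Vd/F for participants whose AUC0-∞ and Ke it declares unfit to summarise. That is an inconsistency in a rule the protocol states, resting only on the standard definitions of the two parameters.

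The numerical consequence is conditional. It is nil if nobody exceeds 20%, which is what a 40 h half-life and a 312 h last sample imply. In the assumed scenarios other than the most adverse, the base-case shifts stay below 1% for CL/F and below 3% for Vd/F. The most adverse figures (-7.0% and +10.4%) need a Cmax only twice the endogenous baseline, a 20% assay CV and no criterion for the terminal fit. No conclusion of the trial turns on this.

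**What to change.** Reword the last sentence of that paragraph of 9.3.3 so that, when AUC%Extrap > 20%, AUC0-∞, t1/2, Ke, CL/F, Vd/F and AUC%Extrap (and MRT if it is extrapolated to infinity) are listed but not summarised. Withholding AUC%Extrap itself is already in the text and can stay.

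The cost is one sentence, settled before data are seen, and a slightly smaller n for CL/F and Vd/F, equal to that of AUC0-∞. The change puts all extrapolation-dependent parameters on the same participants; it does not correct the bias from subtracting a single pre-dose value.

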Participants will undergo screening, admission (baseline), administration and follow-up observation period. Participants will sign an informed consent form before any study procedures are performed. During screening, all participants will be screened for study eligibility within 28 days prior to administration. Eligible participants will be admitted to the clinical study ward no later than one day prior to dosing (D-1). Participants need to fast for at least 10 hours prior to dosing and 4 hours after dosing. Single abdominal subcutaneous injection of the study drug will be given on D1. The administration and follow-up observation period will be 29 days (D1~D29). Participants may be discharged at D7 at the judgment of the investigator. PK blood samples will be collected from D-1 to D14, tolerance and safety will be observed from D1 to D29, and blood samples for PD and anti-drug antibody (ADA) will be collected from screening to D29. After completion of relevant assessments on D29, participants will be considered as having completed this study.

Design of PK study

PK study is required for all participants in this study. PK blood samples will be collected at the following specified time points: D-1, before administration (D1), 2 h, 5 h, 8 h, 10 h, 12 h, 16 h, 24 h, 36 h, 48 h, 72 h, 96 h, 120 h, 144 h, 168 h, 216 h, 264 h and 312 h after administration.

Design of PD study

PD blood samples will be collected from participants in this study at specified time points: D-28 ~ D-2, D-1, D4, D8, D10, D14, D22 and D29; PD blood samples will be collected in the early morning for hematology, in which platelet count will be taken as PD indicator.

Design of immunogenicity study

Immunogenicity blood samples will be collected from participants in this study at specified time points: D-1, D14, and D29. Samples may be further characterized to determine the titer and the presence of neutralizing antibodies (NAb) if positive for ADA.

Data Monitoring / Other Committee: No

Statistical methods:

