3 OBJECTIVES AND ENDPOINTS

Table 5 Objectives and Endpoints

Objectives	Endpoints
Primary	
To evaluate the PK profile following a single dose of rhTPO in healthy Caucasian	PK concentration-time profile and PK parameters: T_{max} , C_{max} , $t_{1/2}$, MRT, AUC_{0-t} , $AUC_{0-\infty}$, V_d/F , K_e , CL/F , $AUC_{\%Extrap}$.
Secondary	
To evaluate the PD profile following a single dose of rhTPO in healthy Caucasian	PLT counts and changes in PLT over time.
To evaluate the safety and tolerability following a single dose of rhTPO in healthy Caucasian	Incidence and severity of AEs and SAEs, physical examination, vital sign, clinical laboratory test, ECG, ISR
To evaluate the immunogenicity profile following a single dose of rhTPO in healthy Caucasian	Incidence of the development of ADAs and NAb (if applicable) to rhTPO

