9.1 Sample Size Determination

This is an exploratory Phase I clinical study of the pharmacokinetics, pharmacodynamics, safety and tolerability of a single dose of Recombinant Human Thrombopoietin for Injection (rhTPO) in a single-center, single-arm, open-label, single-dose design in healthy volunteers from a Caucasian population. The sample size of this study is not based on statistical hypothesis and the study is planned to enrol approximately 22 healthy Caucasian participants.

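### Section 9.3.3 drops AUC%Extrap from its own descriptive statistics above 20%, so the tabulated summary of this primary PK parameter is truncated at 20%

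*Protocol*

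**What the plan says.** Table 5 in Protocol Section 3 gives the primary endpoint as "PK concentration-time profile and PK parameters" and names ten parameters, the last being AUC%Extrap. Section 9.3.3 has it calculated for each participant by non-compartmental analysis, as the "area ratio under extrapolated concentration-time curve". The same section says that arithmetic and geometric means, standard deviations and CVs, with median, quartiles, minimum and maximum, "will be calculated for pharmacokinetic parameters".

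One exception follows. When AUC%Extrap is above 20%, AUC0-∞, t1/2, Ke and AUC%Extrap "will be not analyzed for descriptive statistics but only listed". I read this as applying participant by participant. CL/F and Vd/F are not on the withheld list.

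The Synopsis (Section 1.1) includes a count in the planned output: "Descriptive statistics will be performed for pharmacokinetic parameters, such as number of observations, arithmetic mean, standard deviation". Section 9.3.1 also lists the number of cases among its standard statistics. No count or percentage of participants above the 20% limit is planned.

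**The concern.** Withholding AUC0-∞, t1/2 and Ke above the limit is coherent, because those estimates become unreliable when much of the curve is extrapolated. AUC%Extrap is different in kind. A high value is the diagnostic result that the parameter exists to give. If high values are removed from the parameter's own summary, the summary describes only the participants who passed, and its location and spread are biased towards good coverage.

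This matters most for CL/F and Vd/F. Both depend on the extrapolated part of the curve, and both stay in the summary for the participants above 20%. A reader who checks the AUC%Extrap row to see how far to trust the CL/F and Vd/F rows would be looking at a smaller, selected group. The study has no hypothesis test, so the descriptive tables are the main quantitative output for the primary endpoint.

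**Working it through.** The protocol states no figure for expected extrapolation, so there is none to reproduce. The check has three steps.

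**1. The truncation follows from the rule alone.** The summary set is the participants with AUC%Extrap ≤ 20%. Every mean, quartile and maximum over that set is therefore ≤ 20%. No distributional assumption is needed.

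**2. When would the rule act, on the protocol's own figures?**

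Inputs:
- rhTPO is described "with a half-life of approximately 40 hours" (Section 2.2.1).
- The last PK samples are at "216 h, 264 h and 312 h after administration" (Synopsis; also Table 2).
- AUC0-t stops at the last measurable concentration, and post-dose values are corrected by subtracting the pre-dose value where that is quantifiable (Section 9.3.3).

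With a mono-exponential curve, the fraction beyond time t is 2^(−t/40).
- At t = 312 h: 312/40 = 7.8 half-lives, and 2^(−7.8) = 0.45%.
- For 20%: t = 40 × log2(5) = 92.9 h.

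With one-compartment subcutaneous absorption, the fraction is (ka·e^(−kt) − k·e^(−ka·t))/(ka − k), where k = ln2/40. The absorption half-lives below are assumptions.

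| Last measurable time | Mono-exponential | 2 h | 5 h | 10 h |
|---|---|---|---|---|
| 96 h | 18.9% | 19.9% | 21.7% | 25.2% |
| 120 h | 12.5% | 13.2% | 14.3% | 16.7% |
| 312 h | 0.45% | 0.47% | 0.51% | 0.60% |

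The limit is crossed when the measurable profile ends at about 93–96 h or earlier. With a 10 h absorption half-life the crossing is slightly later, at about 96 + 40 × log2(25.2/20) ≈ 109 h. If concentrations stayed measurable to 312 h, the half-life would have to exceed 312/log2(5) ≈ 134 h for the schedule itself to leave more than 20%.

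The protocol gives neither the LLOQ nor the endogenous TPO level, so the frequency of early loss of the tail cannot be estimated from it.

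**3. How large is the distortion if the rule does act?** This step is assumption only. Take 22 participants (Section 9.1: "the study is planned to enrol approximately 22 healthy Caucasian participants") and a lognormal AUC%Extrap with geometric CV 60%, so s = √ln(1 + 0.6²) = 0.5545. For median m:
- expected number dropped = 22 × [1 − Φ(ln(20/m)/s)]
- full mean = m·e^(s²/2)
- tabulated mean = full mean × Φ((ln(20/m) − s²)/s) / Φ(ln(20/m)/s)

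The second column shows when the measurable profile would have to end to give that median, 40 × log2(100/m).

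| Assumed median | Implied end of measurable profile | Dropped of 22 | Full mean | Tabulated mean |
|---|---|---|---|---|
| 5% | 173 h | 0.1 | 5.8% | 5.7% |
| 10% | 133 h | 2.3 | 11.7% | 9.9% |
| 15% | 110 h | 6.6 | 17.5% | 12.2% |
| 20% | 93 h | 11.0 | 23.3% | 13.5% |

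The maximum is affected more than the mean. With median 10% and geometric SD 1.8 (also assumed), simulation gives an expected maximum of 32% over all participants and 18% in the table. At the roughly 0.5% of step 2, nothing is dropped and the two summaries coincide.

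**The case against.** Three objections carry weight.

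- **Nothing is hidden from the report as a whole.** The same sentence keeps values above 20% in the listing. The n for AUC%Extrap would fall below the n for Cmax and AUC0-t. Individual and semi-log concentration curves are planned, and with about 22 participants the listed exceedances can be counted by eye. This stands. A reader might infer that poorly covered profiles can never be seen, or that the report will always declare the extrapolation acceptable. The protocol does not support that, because only the summary statistics are blind to high values. A reduced n, however, gives neither the reason nor the size of the exceedance.
- **The three withheld parameters match.** AUC0-∞, t1/2 and Ke are summarised over the same ≤ 20% group, so the truncated AUC%Extrap summary correctly describes the profiles behind those three rows. This also stands. The mismatch is with CL/F and Vd/F, which are not withheld.
- **The event may not occur.** Sampling runs to 7.8 half-lives. A reader might infer that the sampling schedule is inadequate or that several participants will be lost from the summary. Neither follows from the protocol's figures. Exceedances would come from assay sensitivity or baseline correction, not from the schedule, and the lognormal scenarios are illustrations only.

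What remains is that the protocol provides for this event and handles AUC%Extrap in a way that defeats the purpose of summarising it.

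**Conclusion.** The point holds as a minor one. The truncation of the AUC%Extrap summary at 20% is certain from the wording of Section 9.3.3. Its numerical effect ranges from nil, if concentrations stay measurable to 312 h with a half-life near 40 h, to a material understatement of the mean and maximum if many measurable profiles end by about 93–96 h (slightly later with slow absorption). Where the study will fall in that range cannot be determined from the protocol. No test, sample size or decision rule depends on this summary, and Cmax, Tmax and AUC0-t are untouched by the rule. The timing results assume the stated half-life and a simple exponential tail; the 20% cap itself rests on no assumption.

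**What to change.** In Section 9.3.3, delete AUC%Extrap from the list of parameters withheld above 20%, and leave the rule for AUC0-∞, t1/2 and Ke as it is. State that AUC%Extrap is summarised for every PKPS participant in whom it can be calculated, and add the number and percentage of participants with AUC%Extrap > 20%.

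The cost is one phrase in the protocol and one extra row in the PK parameter table, with no change to sampling or data collection. There are two small downsides. The reported extrapolation may look slightly less favourable. The AUC%Extrap summary may also cover more participants than the AUC0-∞, t1/2 and Ke summaries beside it, so a footnote should say which participants each row includes.
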